##### Dec 2019 - Sep 2020

**Implement formative evaluation with Lifepool:** online survey (N = 391) and focus groups (N = 31) with women from the Lifepool community, to determine acceptability of alcohol and lifestyle health promotion offered within the breast screening setting, and to collaboratively design the health promotion content and research procedures planned for the Phase II trial. Adapt intervention accordingly.

##### Feb 2021 – Nov 2021

**Implement intervention:** recruit 248 participants over 7 months, consent, baseline assessment, deliver alcohol brief intervention (or control), 4-week and 12-week follow-up telephone assessments, data entry.

**(Aug 2021)** Last participant recruited

**(Nov 2021)** Last 12-week follow-up assessment completed

**(Feb - Nov 2021)** Process and impact program evaluation

##### Sep 2021 - Feb 2022

Data cleaning, statistical and qualitative analyses, preparation of publications, finalise VicHealth reporting requirements (i.e. full research final report, research summary), acquittal report to EH Foundation, final report to HRECs, study archiving

**(Aug – Dec 2021)** Implementation maintenance evaluation

## 2 INTRODUCTION AND BACKGROUND

Alcohol use is a major modifiable risk factor for breast cancer in women, even in low amounts, with evidence of a clear dose-response relationship. Indeed, meta-analyses reveal that the relative risk of breast cancer increases by 4%, 23% and 61% for light, moderate and heavy alcohol consumption, respectively (Bagnardi, 2015).

Women who are eligible for mammography are typically aged 50-74 years and, due to their age, are at increased risk for breast cancer (McPherson, 2000; White, 2014). This is a population who are particularly vulnerable to the harmful effects of alcohol. While breast cancer mortality has reduced by 28-30% due to earlier detection (Roder, 2008) and improved treatment protocols (Burton, 2012), a key health promotion and disease prevention strategy is to reduce women's drinking (WHO, 2017).

In Australia, awareness of the link between alcohol and breast cancer is surprisingly low (Bowden, 2014). While recommended upper limits of alcohol use are emerging as too generous, and associated with increased breast cancer risk, this is not widely understood even by health practitioners or policy makers, let alone the general population (Simapivapan, 2017). Low health

---

literacy regarding alcohol is a significant barrier to making informed decisions about reducing one's alcohol use (Rundle-Thiele, 2013).

Risky alcohol use – including daily drinking – is most common and stable among this cohort (AIHW, 2016; Daly, 2009), yet remains largely under-detected (O'Connell 2003). As such, a large proportion of women do not receive information, advice or effective intervention. Delivering a targeted health promotion strategy aimed at reducing alcohol consumption, within the context of an already institutionalised breast screening program, represents a unique opportunity to prevent alcohol-attributable harm in a large population for which there is great potential for health gain.

Internationally, computerised alcohol brief interventions (i.e. feedback on personal drinking levels compared with age/gender norms, alongside information about alcohol risks/harms) have received strong empirical support as a simple, cost-effective method of reducing drinking and related harm (Donoghue, 2014), and one which overcomes the logistical issues of providing intervention within busy healthcare environments.

No evidence currently exists regarding the utility of brief intervention delivered within breast screening services, a setting uniquely positioned to provide timely, strategic public health messages to prevent alcohol-attributable harm. With 240,970 Victorian women undergoing mammography in 2015 (BreastScreen Victoria, 2016), this setting has the potential for extensive reach. The breast screening setting provides a significant opportunity to engage this population in alcohol health promotion, and complements and adds value to this established healthcare service.

Therefore, we seek to conduct the first randomised controlled trial examining the efficacy of a computerised brief intervention in reducing risky drinking identified within a breast screening setting.

### 3 STUDY OBJECTIVES

#### 3.1 Primary aim and hypothesis

***At 4-weeks post-randomisation, proportion of participants in the active condition (relative to control) accurately identifying alcohol as a clear risk factor for breast cancer.***

We hypothesise that at 4-weeks post-randomisation, compared to the control group, a greater proportion of participants receiving alcohol brief intervention will be able to accurately identify alcohol as a clear risk factor for breast cancer.

#### 3.2 Secondary aims and hypotheses

***At 4-weeks post-randomisation:***

- *Change in participants' attitudes regarding alcohol and breast cancer risk (items adapted from previous literature, e.g. Fisher et al. 2017)*

- *Proportion of participants accurately identifying i) the amount of alcohol in an Australian standard drink; ii) the number of standard drinks in an average restaurant serve of red wine; iii) the maximum number of standard drinks per week recommended by current Australian Alcohol Guidelines (multiple choice and open-ended questions, adapted from previous literature, e.g. Bowden et al. 2014)*  
*Proportion of participants who have accessed health information on i) alcohol harms, ii) alcohol and breast cancer risk, and iii) alcohol harm-reduction*

We hypothesise that at 4 weeks post-randomisation, compared to the control group:

- (i) (Among women who drink >10 standard drinks per week at baseline) Participants receiving alcohol brief intervention will be significantly more likely to endorse an attitude of harm reduction toward alcohol and breast cancer risk
- (ii) A significantly greater proportion of participants receiving alcohol brief intervention will be able to accurately identify i) the amount of alcohol in an Australian standard drink; ii) the number of standard drinks in an average restaurant serve of red wine; iii) the maximum number of standard drinks per week recommended by current Australian Alcohol Guidelines
- (iii) (Among women who drink >10 standard drinks per week at baseline) A significantly greater proportion of participants receiving alcohol brief intervention will have accessed health information on i) alcohol harms, ii) alcohol and breast cancer risk, and iii) alcohol harm-reduction

**At 4-weeks and 12-weeks post-randomisation:**

- *Proportion of participants drinking less than or equal to 10 standard drinks per week (i.e. within current Australian Alcohol Guidelines) (14-day Timeline Followback; TLFB)*
- *Among participants who drink more than 10 standard drinks per week at baseline: Proportion of participants drinking less than or equal to 10 standard drinks per week (14-day TLFB)*
- *Change in alcohol consumption (14-day TLFB; AIHW alcohol frequency/quantity items)*
- *Among participants who drink more than 10 standard drinks per week at baseline: Change in alcohol consumption (14-day TLFB; AIHW alcohol frequency/quantity items)*
- *Change in general health (SF-12)*
- *Change in quality of life (EUROHIS-QOL single item)*

We hypothesise that compared to those in the control group, at 4-weeks and 12-weeks post-randomisation:

- (iv) A significantly greater proportion of participants receiving alcohol brief intervention will be drinking less than or equal to 10 standard drinks per week (i.e. within current Australian Alcohol Guidelines)

- 
- (v) Of participants who drink more than 10 standard drinks per week, a significantly greater proportion of those receiving alcohol brief intervention will be drinking less than 10 standard drinks per week
  - (vi) Participants receiving alcohol brief intervention will report significantly greater reductions in alcohol consumption
  - (vii) Of participants who drink more than 10 standard drinks per week, those receiving the alcohol brief intervention will report significantly greater reductions in alcohol consumption
  - (viii) Participants receiving alcohol brief intervention will report significantly greater improvements in general health and quality of life

### 3.3 Feasibility assessment

Feasibility of implementing the alcohol brief intervention in a breast screening setting will be assessed through formative, process and impact evaluation, by examining factors such as:

- (i) The proportion of patients who agree to receive alcohol health promotion
- (ii) Acceptability of the intervention prototype and research procedures
- (iii) Women's attitudes toward receiving alcohol health promotion intervention
- (iv) Staff feedback on alcohol health promotion intervention implemented in the breast screen setting

## 4 STUDY DESIGN

### 4.1 Type of Study

This study is a single site, parallel group, two arm, pragmatic randomised controlled trial (RCT), with participants randomly allocated to receive either:

**Active:** Alcohol brief intervention + lifestyle health promotion

The intervention arm will receive 4 minutes of alcohol brief intervention, and 3 minutes of lifestyle health promotion (physical activity; maintaining a healthy weight), to increase knowledge of how to improve women's health and reduce breast cancer risk. Alcohol and lifestyle information will be delivered by way of an animation on an iPad. Participant responses to questions about current alcohol use will branch to personalised feedback consistent with level of alcohol consumption (i.e. drinking within or above current Australian Alcohol Guidelines).

Take-home pamphlets - a pamphlet summarising the alcohol information presented during the animation, and a pamphlet on nutrition to maintain a healthy weight, will be provided.

**Control:** lifestyle health promotion, not inclusive of alcohol information

The control arm will receive 3 minutes of lifestyle health promotion (physical activity; maintaining a healthy weight) to increase knowledge of how to improve women's health and reduce breast cancer

---

risk, not inclusive of alcohol information. Lifestyle information will be delivered by way of an animation on an iPad.

Take-home pamphlet - a pamphlet on nutrition to maintain a healthy weight will be provided.

#### 4.2 Study Setting

The proposed pilot study will be conducted at Eastern Health's Maroondah BreastScreen. This service has an annual throughput of 29,824 women (~570 per week), making it an ideal setting to test the alcohol brief intervention.

The study will be conducted in line with Eastern Health's COVIDSafe Plan to ensure the safety of Maroondah BreastScreen's clients and staff as well as Researcher 1, who will be recruiting participants and conducting the baseline assessment. COVID-19 safety procedures will include, for example, wearing of masks by the Researcher and participants, using alcohol wipes to clean iPad devices prior to and after each use, the provision of single-use earphones to watch the health promotion video (which women can take home with them), the maintenance of physical distancing and limiting researcher-participant interactions to a maximum of 15 minutes.

### 5 PARTICIPANTS AND RECRUITMENT

#### 5.1 Number of Participants

The study aims to recruit 548 participants (274 participants per trial arm).

#### 5.2 Eligibility Criteria

Individuals will be randomly assigned to one of the study treatments only if they meet eligibility criteria.

##### 5.2.1 Inclusion criteria

Individuals must meet all of the following criteria to be enrolled in this study:

- Female, attending the BreastScreen setting for routine mammography
- Aged 40+ years
- English as a first language or fluent
- Regular access to a telephone
- Able to provide informed consent to participate

Women at any level of alcohol risk, including non-drinkers, will be eligible to participate to determine any change in non-drinking status and other outcomes over time. This approach also serves to negate the stigma that may occur if only women drinking at risky levels are included in the study.

##### 5.2.2 Exclusion criteria

Individuals meeting any of the following criteria will be excluded from the study:

- Hearing impairment sufficient to prohibit a telephone interview
- Pregnancy

- 
- Not able to read or comprehend English to provide informed consent or receive the brief intervention

### 5.3 Recruitment and identification of potential participants

Recruitment will occur at the Maroondah BreastScreen site 2-days per week over 7 months from Feb 2021. Women will be sent a study flyer with their breast screening appointment reminder email 3 days prior to their appointment. Maroondah BreastScreen reception staff will provide a reminder text message or phone call one day prior to recruitment days to flag the study occurring onsite (as well as confirming women's attendance). Upon arrival at Maroondah BreastScreen, the receptionist will query whether women are aware of the study and provide them with a study flyer to read while waiting for their appointment. Study posters will also be visible on the waiting room notice board and in the screening rooms. At the end of the screening appointment, the radiographer will ask whether the client would like to hear more about the study from the onsite researcher / be involved, and if the client agrees or has further questions, the radiographer will introduce the client to Researcher 1. Participation in the study will occur only after the screening appointment is complete. A script has been developed to assist Researcher 1 with discussing the project with potential participants.

### 5.4 Consent

Researcher 1 will either i) provide a verbal explanation of the trial (aims, procedures, risks and benefits), in lay terms, to women who are interested in participating, guided by the participant information sheet; or ii) (if the Researcher is finishing up with another participant) provide a written summary of the trial (aims, procedures, risks and benefits), guided by the participant information sheet. Potential participants will have the opportunity to discuss the trial and ask questions. Participants will be advised that they can withdraw from the study at any time without prejudice and that their decision whether to take part or not to take part, or to take part and then withdraw, will not affect their routine care or their relationship with Maroondah BreastScreen or Eastern Health.

Women who are willing to take part will be asked to provide either i) verbal informed consent to participate in the study, recorded by Researcher 1 in the trial's REDCap electronic data form; or ii) written consent to participate in the study, recorded in paper form. Participants will be asked to provide consent to the following items: 1. I consent to participate in the computer survey and health promotion. 2. I consent to receive two follow-up calls from a study researcher, in 4 and 12 weeks' time. 3. I consent to the information I provide for this project to be used in possible future related projects, as described in the Participant Information Sheet. I understand that future, related projects will only ever use my information in such a way that I cannot be identified.

A copy of the participant information sheet will be provided to the participant. The consent process and participation in study procedures will occur after the participant's breast screen appointment, so as to not interfere with routine service delivery.

#### 5.4.1 Consent to future use of data

As part of informed consent, and outlined in the participant information sheet, participants will be asked to provide their consent for their re-identifiable data (i.e. their name will not be attached to the data, but only by the unique participant code assigned to both personal information and data, making the data technically re-identifiable), to be used in any future, related research projects conducted by the research team or for student projects. Separate ethics approval will be sought for any subsequent, related project requesting to use these data. Security of participant data will be

---

upheld at all times, and persons working with the research team on subsequent, related studies will not ever have access to participants' personal information/identifiable data, nor the spreadsheet containing re-identifiable information.

## 6 RANDOMISATION AND BLINDING

Women who consent to participate will complete a quick demographic questionnaire and a series of brief measures (evaluating alcohol use, alcohol literacy, quality of life and general health) administered by Researcher 1 or partially self-completed if the Researcher is helping another participant, before being provided with an iPad and randomised at a 1:1 ratio (using computer sequenced block randomisation) to receive the computerised active or control condition.

Randomisation will use a standard computer generated "permuted blocks of variable size" scheme for each stratum. Randomisation lists for each stratum will be generated at the start of the study by the data scientist assisting with the development of the iPad intervention and linked to a unique identification code. The data scientist will play no other role in the randomisation. Randomisation will be linked to a unique identification code, which will be in a re-identifiable format.

Participants will be informed that the study is concerned with promoting health across a range of lifestyle factors (e.g. alcohol use, diet/exercise), which accurately corresponds to the planned outcome measures and intervention conditions and therefore will blind participants to group allocation. Intervention and control computer tasks will be visually identical and will be self-paced. The study researcher performing outcome assessments (Researcher 2) is expected to remain blind to trial allocation.

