In general, outcome variables with repeated measurements will be analysed by fitting linear mixed models (for continuous outcomes or outcomes treated as continuous, such as 5-point Likert scales) or (for categorical / binary outcomes) generalised linear mixed models (GLMMs) or generalised additive mixed models (GAMMs), with fixed effects for treatment and time, and their interaction, and random effects for subjects and assessments within subjects, using restricted maximum likelihood (REML) or similar algorithms. These models allow missing values to be accommodated.

These methods will allow the most suitable variance-covariance model for the repeated measures to be selected, using Akaike's Information Criterion, and, if appropriate, commonality of nonlinear trends over time to be explored via splines. The F-test (or equivalent chi square test, t-test of coefficients in logistic regression) will be used to test for an overall group by time interaction in outcomes measured at all three follow-up times (0, 4 and 12 weeks).

Outcomes measured at two or fewer time points

For outcome variables measured at two or fewer time-points, different models will be used, depending on the nature of the outcome variable:

- Where the outcome is binary and proportions are required, a test of change in proportions for categorical outcomes, e.g. the Cochran-Mantel-Haenszel test, will be applied or, if covariates are required in the analysis, logistic regression with random effects for subjects. Such logistic regression models are instances of GLMMs or GAMMs.
- 2. For continuous outcomes or outcomes treated as continuous (such as 5-point Likert scales) linear mixed models will be used (as for outcomes measured at three time-points).
- 3. In simple cases of the preceding points, the analysis may reduce to (in the sense of being equivalent to) a test of whether there is a difference between the two groups (treatment and control) in the changes in the mean (for continuous outcomes). If just one time point is involved, we may use a binomial test of proportions (for categorical outcomes).

Outcomes measured at 4 and 12 weeks but without a baseline measurement will be covered by this case.

Missing values

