Where possible, missing values will be handled under the missing at random assumption; that is, unless there is good reason to believe this assumption is untenable. In cases of doubt the analysis will be re-done with (a) missing values imputed and (b) the corresponding subjects removed from the analysis.

Outcomes where there is no baseline measure possible (that is, by design) will not be treated as having the baseline value missing, but rather as belonging to the two time-point case.

Exploratory analyses

Exploratory analyses will be performed using the same methods as for the primary and secondary outcomes (as appropriate) plus, optionally, such other modelling strategies as may be useful (e.g. random forests or decision trees as exploratory tools, or other classification tools).

In exploratory analyses of outcomes measured at three time-points, mixed models with covariates as relevant (see list of potential covariates below), including their interactions with treatment group, will be fitted in order to identify moderating factors. Categorical, ordinal and binary outcomes will be analysed in a similar way using generalised linear mixed models (GLMMs) or generalised additive mixed models (GAMMs).

In exploratory analyses of outcomes measured at two time-points, logistic regression with random effects for subjects will be utilised to assess the effects of potential covariates (see list of potential covariates below).

Statistical software

Analyses will be conducted using the most appropriate procedures in GenStat, R, SAS or STATA and additional analyses not specified in the published protocol or this addendum will be regarded as exploratory.

Statistical Analysis of the Primary and Key Secondary Outcome Variables

Primary Outcome

The primary analysis will take place after all subjects, not known to have withdrawn or not deemed lost to follow-up, have had their 12-week assessments, based on the intention to treat (ITT) principle (i.e. subjects' data are analysed as randomised and as stratified).

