The primary outcome of this repeated measures RCT is the proportion of participants accurately identifying alcohol as a clear risk factor for breast cancer at 4-weeks post-randomisation. Inferences about the effect of the Health4Her intervention on the primary outcome will be based on a comparison, between treatment groups, of change from baseline to 4-weeks post-randomisation using a Cochran-Mantel-Haenszel test. This analysis tests for homogeneity of the odds ratio across strata (i.e. intervention and control). A binomial test (that is, a test of proportions) will be used as an ancillary analysis of the primary outcome (i.e. the difference in proportions between the two groups at 4-weeks post-randomisation).

Relevant covariates (from the list of potential covariates below) may also be used in further analysis, using generalised linear models (logistic regression) to make comparisons. Additional analyses may use covariates for post-stratification.

Secondary Outcomes

Alcohol Consumption

Alcohol consumption will be assessed by the Alcohol 14-day Timeline Follow-back (TLFB). Heavy drinking days are measured as >40 grams of alcohol (>4 Australian standard drinks). Alcohol consumption will also assessed by the AIHW alcohol frequency quantity items. Assessments are made at 0, 4 and 12 weeks and linear mixed models (continuous variables) or GLMMs or GAMMs (categorical / binary variables) will be used. The following outcomes will be analysed (transformed if necessary for analysis):

Secondary outcome 1 – Proportion of participants drinking less than or equal to 10 standard drinks per week at 4-weeks and 12-weeks post-randomisation. Derived from (operationalised in two ways):

- Has the participant consumed >10 standard drinks in week one AND/OR >10 standard drinks in week two? (tlfb_nhmrc_both_comprh)
- Has the participant consumed >10 standard drinks in both week one AND week two? (derived variable: tlfb_nhmrc_bothwks)

Secondary outcome 2 – Proportion of participants drinking less than or equal to 10 standard drinks per week at 4-weeks and 12-weeks post-randomisation, among only participants who drink more than 10 standard drinks per week at baseline.

Subgroup defined as either i. women who consumed >10 standard drinks in week one AND/OR >10 standard drinks in week two (tlfb_nhmrc_both_comprh) or ii. women who consumed >10 standard drinks in both week one AND week two (tlfb_nhmrc_bothwks).

Outcome derived from:

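### Randomisation is described as stratified and the SAP promises analysis as stratified, but the primary test uses the two arms as its strata and no committed analysis contains the randomisation strata

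*Combined protocol and SAP*

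**What the plan says.** **Allocation.** Protocol section 6 says that women are "randomised at a 1:1 ratio (using computer sequenced block randomisation"), and then describes variable-size permuted blocks within strata: "Randomisation lists for each stratum will be generated at the start of the study". No stratification factor is named there.

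**Principle of analysis.** The SAP, under Primary Outcome, explains intention to treat as meaning that "data are analysed as randomised and as stratified".

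**Primary test.** The same SAP section compares the arms in respect "of change from baseline to 4-weeks post-randomisation using a Cochran-Mantel-Haenszel test" and adds: "This analysis tests for homogeneity of the odds ratio across strata (i.e. intervention and control"). It continues: "A binomial test (that is, a test of proportions) will be used as an ancillary analysis of the primary outcome", meaning the difference between the arms at 4 weeks.

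**Models.** Under the SAP heading for outcomes measured at more than two time points, the mixed models are fitted "with fixed effects for treatment and time, and their interaction, and random effects for subjects and assessments within subjects".

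**Covariates.** Covariate-adjusted logistic regression and post-stratification are permitted for the primary outcome but not required. The candidates come from a closing list headed as exploratory. It includes age and baseline drinking relative to the guidelines, but marks no item as a randomisation factor.

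**The concern.** The two documents make a pair of linked statements: allocation was by stratum, and the analysis respects that. A statistician who then follows the SAP line by line runs no committed analysis in which a randomisation stratum appears. In the one test that has a slot for strata, the slot is filled by treatment arm.

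Two things are at stake. First, a report saying that the data were analysed as stratified would be untrue. Second, stratified allocation balances the strata between arms and so removes between-stratum variation from the difference in proportions. A test that ignores the strata still counts that variation in its standard error, so it can be conservative and give up some power.

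**Working it through.** **1. The plan's sample size (protocol section 14.1).** Inputs: control 0.22, active 0.34, two-sided alpha 0.05, power 80%, attrition 20%. With mean proportion 0.28, the pooled-variance formula without continuity correction is

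n = [1.96 × √(2 × 0.28 × 0.72) + 0.842 × √(0.22 × 0.78 + 0.34 × 0.66)]² / 0.12² = 218.6, so 219 per arm.

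219 / 0.8 = 273.75, so 274 per arm and 548 in total. This matches the protocol. The calculation is for an unstratified comparison of two proportions, so no gain from stratification was built in.

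**2. What ignoring strata could cost the ancillary test.** The SAP reports 279 randomised per arm; 80% of that is 223. The effect of the strata on the outcome is not given. *Assumption:* two equal strata, with risks d below and d above the arm mean, and a constant difference of 0.12.

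- Unstratified variance × n: U = 0.22 × 0.78 + 0.34 × 0.66 = 0.1716 + 0.2244 = 0.3960.
- Variance × n within strata: S = U − 2d².
- SE_u = √(U/223) = 0.0421; SE_s = √(S/223).
- True type I error of the unstratified test: 2 × [1 − Φ(1.96 × √(0.1716 / (0.1716 − d²)))].
- Power: unstratified Φ((0.12 − 1.96 SE_u)/SE_s); stratified Φ(0.12/SE_s − 1.96).

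| Control risks in the two strata | S | U/S | Type I error, unstratified | Power, unstratified v stratified |
|---|---|---|---|---|
| 0.17 / 0.27 (d = 0.05) | 0.391 | 1.013 | 4.8% | 81.4% v 81.7% |
| 0.12 / 0.32 (d = 0.10) | 0.376 | 1.053 | 4.3% | 81.9% v 83.2% |
| 0.07 / 0.37 (d = 0.15) | 0.351 | 1.128 | 3.5% | 82.7% v 85.6% |

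At d = 0 the ratio is 1 and nothing is lost.

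**3. Log-odds scale.** With 219 per arm and a stratum-outcome odds ratio of 2.7, the unadjusted log odds ratio is 0.602 (SE 0.217, z = 2.78). Adjusted for stratum it is 0.632 (SE 0.222, z = 2.84). The adjusted SE is larger; only z improves.

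**4. Linear mixed models.** The planned test is the group-by-time interaction, a within-woman contrast. A stratum effect that is constant over time cancels from each woman's change. In a simulated trial (446 women, three visits, complete data, strata balanced by arm, large stratum effect) the interaction SE was 0.14355 with and without a stratum term.

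**5. The primary CMH as written.** With arms as strata and visit (baseline or week 4) as the row, the CMH statistic pools the change over time across arms. Take 219 per arm and, for illustration, treat the visits as independent.

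- Both arms rise from 0.22 to 0.34, so there is no intervention effect. In each arm the week-4 count is 74.46 against 61.32 expected, an excess of 13.14 with variance 22.13. Chi-square = 26.28² / 44.25 = 15.6.
- The active arm rises and the control arm falls by 12 points. The excesses are +13.14 and −13.14, and chi-square = 0.

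The statistic thus responds to a common time effect, not to a difference between arms. Homogeneity of odds ratios, which the SAP sentence describes, is a different test (Breslow-Day, for example). The type I errors in step 2 therefore say nothing about the primary test.

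**The case against.** A reader might infer more: that standard errors throughout the trial are too wide, that the primary test's type I error is below 5%, and that power already paid for is being thrown away. The documents do not support this.

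- **Standard errors.** A wider SE needs strata that predict the outcome and an analysis on the scale of a difference in proportions or means between women. The first is unknown. The second excludes the logistic models and GLMMs (step 3) and the planned interaction test in the linear mixed models (step 4).
- **Type I error.** The figures in step 2 belong to the ancillary test of proportions. Step 5 shows that the primary CMH as written addresses another question altogether.
- **Power.** The 548 comes from an unstratified formula, and in every assumed scenario unstratified power stays above the planned 80%. What is forgone is a bonus.

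Two further points have force. The baseline answer, which ought to be in the primary comparison anyway, would probably absorb part of any stratum effect, so the extra gain from the strata may be smaller than the table shows. And the optional covariates may happen to include the stratification factors. Nobody can tell without their names, and we do not claim that they are recorded nowhere: the section 8.1 flow chart and some administrative pages are not in the text available.

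All of this limits the size of the point. It does not remove the mismatch, because a permitted exploratory adjustment is not a commitment to analyse as stratified.

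**Conclusion.** The point holds as an internal inconsistency, which needs no assumption to see: stratified allocation, a promise of stratified analysis, and no committed analysis that contains the strata.

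The statistical cost is conditional. For the ancillary comparison of 4-week proportions it runs from nil to a variance overstated by about 13% and about 3 points of power (82.7% v 85.6%), assuming two equal strata up to 30 points apart in control risk and 223 analysed per arm. For that test the direction is conservative.

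The more practical reason to act is that the strata slot of the primary CMH holds the wrong variable. Putting the randomisation factors there, with arm as the exposure, corrects that too.

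**What to change.** Before outcomes are compared by arm, revise the SAP as follows.

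1. Identify the stratification factors from the allocation list and name them.
2. For the primary analysis, make arm the exposure and 4-week response the outcome. Define the CMH strata by the randomisation factors and the baseline answer. Alternatively, use logistic regression with arm, baseline answer and the stratification factors.
3. Use the same factors in the other between-arm comparisons of proportions: the ancillary 4-week test and secondary outcomes 6 and 7. Adding them to the linear mixed models is harmless, but should not be expected to sharpen the interaction test.
4. If allocation was not in fact stratified, remove the references to strata from protocol section 6 and from the SAP's definition of intention to treat.

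This is a free improvement. It costs a few sentences in the SAP and needs no new data, since any strata are already on the randomisation list.
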